#### 8.3.3.3. Supplementary Analyses

The supplementary Estimand for the change from baseline in post-bronchodilator  $FEV_1$  (L) at Week 52 is the On-IP Estimand (see Section 2) and will utilize the ITT Analysis Set (see Section 5.2). The same model as used for the main analysis will be implemented for this Estimand (see Section 8.3.3.1).

#### 8.3.4. Annualized Rate of Severe Pulmonary Exacerbations

#### 8.3.4.1. Main Analyses

The Estimand of the Annualized Rate of Severe PEs is the On-Study Estimand in which all observed data will be included in the analysis (see Section 2). The ITT Analysis Set (see Section 5.2) will be used for this Estimand. The derivation of the endpoint is detailed in Section 6.7.4.

CONFIDENTIAL Page 61 of 139

The analytical approach as outlined for the primary endpoint in Section 8.2.1 will be applied to the Annualized Rate of Severe PEs. The rate ratios for comparison between treatments and their 95% Cis will be presented along with the corresponding Wald p-value.

### **8.3.4.2.** Sensitivity Analyses

The analytical approach of the sensitivity analysis described in Section 8.2.2 will be applied for severe PEs with the difference, that death from any cause will be counted as a severe PE.

#### 8.3.4.3. Supplementary Analyses

The supplementary Estimand for the Annualized Rate of Severe PEs is the On-IP Estimand (see Section 2) and will utilize the ITT Analysis Set (see Section 5.2). The same negative binomial regression model as applied for the primary analysis will be implemented for this Estimand (see Section 8.2.1).

## 8.3.5. Change from Baseline in QoL-B Respiratory Symptoms Domain Score at Week 52

The QoL-B is a validated, self-administered, patient reported outcome questionnaire used to assess symptoms, functioning, and health related quality of life in adults with non-CF bronchiectasis (Quittner, 2015). It measures outcomes over a recall period of 1 week. The questionnaire contains 37 items on 8 scales (physical, role, vitality, emotional, social, treatment burden, health perception, and respiratory).

There is no total score for QoL-B. Calculation of scale (domain) scores is described in Appendix A.

#### 8.3.5.1. Main Analyses

The Main Estimand of the change from baseline in QoL-B Respiratory Symptoms Domain Score at Week 52 is the On-Study Estimand in which all observed data will be included in the analysis (see Section 2). The population attribute for this Estimand is adult participants with NCFBE who meet all inclusion criteria and none of the exclusion criteria. The ITT Analysis Set (see Section 5.2) will be used for this Estimand.

Calculated Respiratory Symptoms score (items 29 to 37) will be summarized at baseline and change from baseline at Week 52 by treatment group using descriptive statistics. Single item responses (each question) will be summarized by treatment group in a shift table. Completion rates will be presented by time point (see Section 6.7.5.10).

Change from baseline of calculated Respiratory Symptoms score (items 29 to 37) at Week 52 will be analyzed using a linear repeated measures model including treatment group, visit, treatment-by-visit interaction, sputum sample being classified as positive or negative for *Pseudomonas aeruginosa* at Screening Visit, the number of prior PEs [<3, ≥3] in the previous 12 months and stratification region (North America, Europe, Japan, and the Rest of the World) as fixed effects, and baseline value as covariate. Given that the QoL-B will be administered every two weeks for a total of 26 time points, estimation of a complex variance-covariance structure with many parameters will be untenable. Therefore, the variance-covariance structure will be compound symmetric with the robust sandwich variance

CONFIDENTIAL Page 62 of 139

estimator. Results will be presented in the same manner as the analysis of "Change from Baseline in Post-bronchodilator FEV1 (L) at Week 52" (see Section 8.3.3), including a figure displaying the adjusted means and corresponding 95% confidence intervals at Week 52 by treatment group. The OM option will be used to adjust the co-efficients for the LSMEANS to reflect the observed data. The between-treatment differences and corresponding 95% CIs will be presented; the associated p-value for the adjusted mean difference will be compared to the appropriate alpha level per the multiple test procedure.

If the model fails to achieve convergence, similar handling described in Section 8.3.1.1 Main analysis for Change from Baseline in Post-bronchodilator FEV1 (L) at Week 52 will be applied and the adjustment will be added to the footnote of the corresponding outputs.

#### 8.3.5.2. Sensitivity Analyses

The analytical approach of the sensitivity analysis described in Section 8.3.3.2 will be applied for the change from baseline in QoL-B Respiratory Symptoms Domain Score at Week 52.

#### 8.3.5.3. Supplementary Analyses

The supplementary Estimand for the change from baseline in QoL-B Respiratory Symptoms Domain Score at Week 52 is the On-IP Estimand (see Section 2) and will utilize the ITT Analysis Set (see Section 5.2). Technical details for the implementation in SAS can be found in Appendix I.

The same linear model as used for the main analysis will be implemented for this Estimand (see Section 8.3.5.1).

As there is no universally accepted meaningful change threshold that can be prespecified for responder analyses of the Qol-B Respiratory Symptoms domain score, cumulative responder curves (Farrar et al. 2006) will be generated for the On-IP Estimand. Change from baseline at Week 52 will be plotted on the x-axis, and the proportion of responders (i.e., participants that equal or exceed that level of change) on the y-axis. A separate curve will be produced for each treatment on the same graph. Participants with missing data will be considered non-responders. Pairwise comparisons of the cumulative responder curves will be conducted using the Kolmogorov-Smirnov test.

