e Vital signs and clinical laboratory blood samples will be collected at the Screening Visit and prior to the first dose of the study drug on Day 1 (Baseline), and at every in-clinic visit. Vital signs include the following: systolic and diastolic blood pressure, respiratory rate (breaths per minute), pulse (beats per minute), body temperature (°C), and oxygen saturation. Clinical laboratory parameters are listed in Table 6.

f Clinical laboratory blood samples should be collected in a fasted state (after an overnight fast for morning sample collection or at least 4 hours without food at other times) if possible.

<sup>g Spirometry will be performed preferably in the morning (at the same time of day each time) and performed after withholding the last dose of SABA for 6 hours, or LABA for 12 hours or LAMA for 24 hours or ultra-long LABA for 24 hours.

- OBEST questionnaire: Adult subjects should complete the BEST questionnaire (in the evening) on an electronic diary DAILY from the Screening Visit through EOS Visit (Week 56). If there is an increase of symptoms (as per the algorithm programmed in the electronic data capture system) the site and the subject will be alerted. The subject will be asked to contact the site within 1 business day and the site will receive a message to contact the subject within 1 business day. The goal is to assess if a pulmonary exacerbation or any other medically relevant event is taking place. Subjects should be trained on completion of the questionnaires at Visit 1 (Screening). Subjects should be retrained if the compliance falls below 75% between each on-site visit after randomization.
- p QOL-B: where validated translations are available in the local language, all adult subjects will complete the QOL-B on an electronic diary on Day 1 (Baseline) and every 2 weeks thereafter through Week 56. The QOL-B is considered "modified" because the first page, which only collects demographics information, will be deleted from the questionnaire since demographics are collected on the appropriate eCRF page instead.
- q PGI-S and PGI-C: Newly enrolled adult subjects will complete the PGI-S and PGI-C on an electronic device where validated translations are available in the local language. Existing subjects will not complete the PGI-S and PGI-C.

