		Supplementary: On-IP	Randomized IP regardless of modifications to standard of care	Early discontinuation from randomized IP / While On-Treatment Modification to standard of care / Treatment Policy	8.3.4.3
Change from Baseline in Quality of Life Questionnaire	Mean Difference	Primary: On- Study	Assignment to IP regardless of discontinuation or modifications to standard of care	Early discontinuation from randomized IP / Treatment Policy Modification to standard of care / Treatment Policy	8.3.5.1
Bronchiectasis		Supplementary: On-IP	Randomized IP regardless of modifications to standard of care	Early discontinuation from randomized IP / While On-Treatment	8.3.5.3

CONFIDENTIAL Page 16 of 139

Brensocatib (INS1007)

Statistical Analysis Plan: INS1007-301 FINAL Version 1.0 16 APR 2024

(QoL-B)	Modification to standard of care /
Respiratory	Treatment Policy
Symptoms	
Domain Score	
at Week 52*	

\* The population for Change in QoL-B Respiratory Symptoms Domain Score at Week 52 will be adult participants with NCFBE

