## 6.4.3. Baseline Definition, Change from Baseline

According to Table 5 of the CSP ("Schedule of Assessments and Procedures"), the second visit (V2) is defined as "Baseline". However, the definition of the "Baseline" which is used to

CONFIDENTIAL Page 32 of 139

derive any changes of assessments during study conduct, e.g., laboratory parameters, depends on the timing of the first IP administration and can therefore be different from Baseline/Day 1/Visit 2. Therefore, unless otherwise stated, for the purpose of analysis baseline value is the last non-missing value prior to or at the date of the first dose of IP, considering also unscheduled visits. For participants who do not receive IP during the study, baseline is defined as the latest, non-missing collected value on or before Study Day 1.

Change from baseline will only be calculated for measures that have post-baseline records. Change from baseline is calculated as:

visit value – baseline value.

If either the baseline or visit value is missing, the change from baseline will be set to missing as well.

For summaries, whenever baseline is presented, the above baseline definition is used. That is, the baseline summary presented is in general not the summary of the (CSP defined) Baseline/Day 1 visit. Screening values will be listed but not summarized. Throughout the document, Baseline (capital B) refers to the visit Baseline/Day 1; baseline (lower case b) refers to the values derived using the baseline definition above.

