### 8.3.5.4. Identification of the Meaningful Change Threshold

The meaningful change threshold (MCT) will be estimated from the ASPEN data by applying an anchor-based approach using the PGI-S and PGI-C assessments as anchors at Week 52. The MCT will be supplemented with distribution-based analyses, empirical cumulative distribution function (eCDF) curves, and probability density function (ePDF) curves to provide supportive information. All treatment groups will be pooled. The MCT evaluation will be addressed in a separate document.

Responder status for Change from Baseline in QoL-B Respiratory Symptoms Domain Score at Week 52 will be determined utilizing the identified MCT. Participants with QoL-B Respiratory Symptoms Domain Score missing at Week 52 and available at Baseline will be considered as non-responders, while participants with QoL-B Respiratory Symptoms Domain Score missing at Baseline will be excluded from the analysis. Statistical analysis for the

CONFIDENTIAL Page 63 of 139

responder status will be similar to the main analysis approach for the secondary endpoint of Responder Status for exacerbation-free over the 52-week treatment period.

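### The QoL-B cumulative responder curves and their Kolmogorov-Smirnov test count adults with no baseline score as non-responders, contrary to SAP 8.3.5.4, and are labelled On-IP although they compare a composite of change and retention

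*SAP*

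**What the plan says.** - **Missing-data rule and test.** SAP 8.3.5.3 plots, for each level of Week 52 change, the proportion of participants who reach it. It states "Participants with missing data will be considered non-responders. Pairwise comparisons of the cumulative responder curves will be conducted using the Kolmogorov-Smirnov test". The Appendix I graph (Exploratory assessments) repeats the missing-data rule. Neither place makes an exception.
- **Estimand label.** The curves are specified for the On-IP Estimand, in the ITT Analysis Set. For QoL-B, SAP Table 2 gives the On-IP strategy as "Early discontinuation from randomized IP / While On-Treatment".
- **Change score without a baseline.** SAP 6.4.3: "If either the baseline or visit value is missing, the change from baseline will be set to missing as well".
- **Who receives the questionnaire.** Protocol Table 5, in the QOL-B footnote: "where validated translations are available in the local language, all adult subjects will complete the QOL-B on an electronic diary".
- **The neighbouring responder analysis.** SAP 8.3.5.4 counts adults with a baseline but no Week 52 score as non-responders, but "participants with QoL-B Respiratory Symptoms Domain Score missing at Baseline will be excluded from the analysis".

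**The concern.** Two separate things are mixed into the curves.

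The first is a baseline problem. An adult who never received the QoL-B has no change score. With no baseline condition, that adult sits below the lowest threshold on the graph and counts as a failure everywhere, including at thresholds that allow a large worsening. Such adults carry no information on treatment, and the next section removes them. The SAP therefore has two rules for the same score.

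The second is a labelling problem. An adult who stops IP well before Week 52 has no on-IP Week 52 score, and SAP 6.4.9 does not re-allocate the two-weekly questionnaires. That adult is also placed below every threshold. The quantity compared is then change in score combined with availability of an on-IP score. This is a composite, although the label says While On-Treatment. SAP 8.3.5.3 uses these curves because no meaningful change threshold is accepted in advance, so a reader could take the p-value as threshold-free evidence about symptoms alone.

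**Working it through.** The documents state no alpha, power, missing rate, SD or effect size for this test, so there is no planned figure to reproduce.

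**Inputs from the documents:** 540 adults per arm (SAP 3.1); two-sided p-values (SAP 6.1); nine items scored 1 to 4 on a 0 to 100 scale (SAP Appendix A), so score steps of 100/27 = 3.7.

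**Assumed inputs:** alpha 0.05, change SD 18, missing shares as shown, missingness unrelated to the score, asymptotic test, 3,000 simulated trials per scenario.

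**1. Structure.** Let m be the share missing at Week 52 and G the distribution of change among those observed. With missing scores below every threshold, F = m + (1 − m)G.
- If G is the same in both arms, the largest distance between the curves is D = |m1 − m2|, which is retention only.
- If m is the same in both arms, D = (1 − m) × D0, where D0 is the true distance.
- The 5% critical value at 540 per arm is 1.358 × √(2/540) = 0.083.

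**2. Adults with no baseline.** Let b be their share, equal in both arms, and m the further share missing.
- As written: D = (1 − b)(1 − m)D0, with 540 per arm.
- With the 8.3.5.4 exclusion: D = (1 − m)D0, with 540(1 − b) per arm.
- Relative to its own critical value, D as written is smaller by the factor √(1 − b): 0.95 at b = 10% and 0.89 at b = 20%.

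For a normal shift of 0.25 SD, D0 = 2Φ(0.125) − 1 = 0.0995. With m = 15%:
- b = 10%, as written: 0.90 × 0.85 × 0.0995 = 0.076, against 0.083.
- b = 10%, excluded: 0.85 × 0.0995 = 0.085, against 1.358 × √(2/486) = 0.087.

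Simulated power with m = 15%:

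| No baseline | 0.20 SD, as written | 0.20 SD, excluded | 0.25 SD, as written | 0.25 SD, excluded |
|---|---|---|---|---|
| 5% | 47% | 50% | 66% | 69% |
| 10% | 39% | 44% | 60% | 67% |
| 20% | 30% | 39% | 48% | 61% |

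With no true effect, rejection as written is 2.0 to 2.2% in all three rows. Adults with no baseline dilute the comparison; they do not create false rejections.

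**3. Retention gap with identical score change.**

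| Missing, arm 1 v arm 2 | Rejection as written |
|---|---|
| 15% v 15% | 2.4% |
| 15% v 18% | 7.9% |
| 15% v 20% | 21.5% |
| 15% v 25% | 85% |

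A second set of simulations gives about 7% for a 3-point gap. The baseline filter does not remove this: with 10% lacking a baseline and 15% v 25% missing, rejection is 73% as written and 81% with the filter.

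**The case against.** The strongest defence is that counting dropouts as non-responders is a declared and recognised composite convention. The test compares exactly the curves that the SAP defines, and SAP 8.3.5.4 treats adults missing at Week 52 in the same way. That stands. What it does not answer is the On-IP label, or the missing baseline condition.

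It is also fair that retention is reported elsewhere: completion rates by time point and treatment group (SAP 6.7.5.10 and 8.3.5.1) and intercurrent events by arm (SAP 8.4). This helps a careful reader. However, completion is a ratio of instruments received to instruments expected, which need not equal the share missing from these curves.

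A reader might infer that the test is invalid and should be replaced by one on observed on-IP changes. The documents do not support that. At equal missingness the planned test is slightly conservative. The observed-score test conditions on staying on drug, and its level of about 2% relies on missingness unrelated to the score. With 20% missing in each arm, score-related in one arm only (assumed logistic slope 1.5 per SD, SD 16), and identical underlying change, the observed-score test rejects 76% of the time and the planned test 62%. It would also depart from the Week 52 rule in 8.3.5.4.

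A reader might also take the 85% figure as a forecast. It needs a 10-point retention gap, and no passage suggests one. Protocol 1.2.2.3 reports that the number of Phase 2 subjects with adverse events leading to study discontinuation was similar across groups.

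**Conclusion.** The point holds as a minor one, in two parts.

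- **Baseline condition.** As worded, SAP 8.3.5.3 and Appendix I count adults with no baseline as non-responders at every threshold, and SAP 8.3.5.4 excludes them. The text does not name these adults; the reading follows from the unqualified rule together with SAP 6.4.3. Under the assumptions above, the cost is about 5 to 7 points of power if 10% lack a baseline and 9 to 13 points if 20% do. The documents do not give the true share.
- **Label.** The curves and test compare a composite of change and on-IP availability under a While On-Treatment label. A retention gap alone can drive rejection: about 7 to 8% at 3 points and 22% at 5. With equal missingness the level is held.

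It would be wrong to infer that confirmatory inference is at risk. The Kolmogorov-Smirnov test is supplementary and lies outside the 12 hypotheses in SAP 6.3. The QoL-B secondary endpoint is tested by the On-Study repeated-measures model, with its own tipping-point analysis.

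**What to change.** In SAP 8.3.5.3 and the Appendix I graph:

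1. Restrict the curves and the Kolmogorov-Smirnov test to adults with a baseline QoL-B Respiratory Symptoms score, as SAP 8.3.5.4 already does.
2. Label the curves and the test as a composite of score change and retention. Avoid the bare term Composite Estimand: SAP Section 2 uses it for the exacerbation-free endpoint, with non-response imputed only for failure-type events.
3. Print the share missing at Week 52 by arm with the figure. This is needed because the baseline filter leaves the retention effect in place.

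A Kolmogorov-Smirnov test on observed on-IP changes may be added as a secondary display, but should not replace the planned test.

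The cost is a few lines of SAP wording, one filter on a baseline variable and one added row in the figure. No new data are needed.

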### 8.3.5.4. Identification of the Meaningful Change Threshold

The meaningful change threshold (MCT) will be estimated from the ASPEN data by applying an anchor-based approach using the PGI-S and PGI-C assessments as anchors at Week 52. The MCT will be supplemented with distribution-based analyses, empirical cumulative distribution function (eCDF) curves, and probability density function (ePDF) curves to provide supportive information. All treatment groups will be pooled. The MCT evaluation will be addressed in a separate document.

Responder status for Change from Baseline in QoL-B Respiratory Symptoms Domain Score at Week 52 will be determined utilizing the identified MCT. Participants with QoL-B Respiratory Symptoms Domain Score missing at Week 52 and available at Baseline will be considered as non-responders, while participants with QoL-B Respiratory Symptoms Domain Score missing at Baseline will be excluded from the analysis. Statistical analysis for the

CONFIDENTIAL Page 63 of 139

responder status will be similar to the main analysis approach for the secondary endpoint of Responder Status for exacerbation-free over the 52-week treatment period.

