### 7.3. Demographic and Baseline Characteristics

Demographic and baseline characteristic variables will be summarized for all Analysis Sets as defined in Section 5. A summary by region will be provided, too. The summary will include:

Insmed Incorporated

- country,
- age,
- age group (12 to <18 years, 18 to <65 years, >= 65 years),
- age group >=18 years,
- age group (<75 years, >=75 years),
- sex,
- ethnicity,
- race,
- Baseline height,
- Baseline BMI,
- Baseline FEV1, pre- and post-bronchodilator (in L and % Predicted),
- Baseline FEV1 (% Predicted) < 50%,
- History of Chronic Obstructive Pulmonary Disease, identified through MedDRA coded terms (see Appendix K),
- History of Asthma, identified through MedDRA coded terms (see Appendix K),
- Hospitalized in prior 24 months for PE,
- CT Scan confirmation of Bronchiectasis,
- Use of Inhaled Steroids, identified through ATC coded terms (see Appendix K),
- Chronic use of Antibiotics,
- Bronchiectasis Severity Index (BSI) (see Appendix L),
- BSI categories (<=4, 5-8, >=9),
- Smoking status, including pack-years smoked (refer to Section 6.4.6 for calculation of pack-years smoked),
- Baseline eosinophil count (>=300/mm3, <300/mm3),
- Baseline QoL-B Respiratory Symptoms Domain Score (adults),
- Baseline BE-CT Score
- the stratification variables region (North America, Europe, Japan, and Rest of World), sputum sample (positive or negative for *Pseudomonas aeruginosa*) and the number of PEs in the previous 12 months (<3, >=3). Stratification variables will be presented as used for randomization.
- Geographic Region (South America, Eastern Europe, Western Countries, Asian Countries)

The distribution of participants randomized across region, country, and site will be presented for the ITT analysis set.

In addition, a listing will be produced for mismatches between randomized and actual strata.

CONFIDENTIAL Page 50 of 139

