#### 8.3.2. Responder Status for Exacerbation-Free over the 52-Week Treatment Period

#### 8.3.2.1. Main Analyses

The Estimand of the responder status for exacerbation-free over the 52-week treatment period is the On-Study Estimand in which all observed data will be included in the analysis (see Section 2). The ITT Analysis Set (see Section 5.2) will be used for this Estimand. The derivation of the endpoint is detailed in Section 6.7.2.

The number and percentage of Responders/Non-responders over the 52-Week Treatment Period will be presented by treatment group.

Responder status at Week 52 will be compared between treatment groups brensocatib vs. placebo using a logistic regression model including treatment group, sputum sample being classified as positive or negative for *Pseudomonas aeruginosa* at Screening Visit, the number of prior PEs [<3 or ≥3] in the previous 12 months, stratification region (North America, Europe, Japan, and the Rest of the World), and age group (adult, adolescent) as fixed effects. If the age group covariate creates estimability issues, it may be removed. An estimate of the odds ratio for the treatment comparison (brensocatib 10mg vs. placebo; brensocatib 25mg vs. placebo) and the 95% Wald confidence interval will be summarized; the corresponding p-value from the Wald chi-square test will be compared to the appropriate alpha level per the multiple test procedure.

For participants who discontinue the study prior to Week 52 without having experienced a PE confirmed through adjudication, their responder status will be missing. To address this issue, first event times for these participants will be imputed based on the observed data model for the time period after discontinuation from the trial. If the imputed event time occurs prior to Week 52, the participant will be considered a non-responder. Otherwise, the participant will be considered a responder. The process of imputing missing PE data will be repeated multiple times to create 100 separate datasets. With each increment, the 100 complete data sets will each be analyzed using the logistic regression model described above. The analysis results will then be combined using Rubin's rules (Rubin 1987).

Technical details for the implementation in SAS can be found in Appendix I.

CONFIDENTIAL Page 59 of 139

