#### **Scale scores**

Each of the 8 domain scores is standardized on a 0 to 100-point scale with higher scores representing fewer symptoms or better functioning and quality of life.

Scale scores are derived from a subset of items and calculated by

$$scale\ score = \frac{mean\ of\ responses - 1}{3} * 100$$

Contributing items:

Table 12: QoL-B Items Contributing to Domain Score Calculation

Domain	#items	Contributing items	Allowed #missing items*
Physical Functioning	5	1, 2, 3, 4, 16	2
Role Functioning	5	17, 20, 25, 27, 28	2
Vitality	3	6, 8, 9	1
Emotional Functioning	4	7, 10, 11, 23	2
Social Functioning	4	18, 19, 22, 26	2
Treatment Burden	3	12, 13, 14	1
Health Perceptions	4	5, 15, 21, 24	2
Respiratory Symptoms	9	29 to 37	4

\*If more missing items are observed than allowed, the domain will not be scored.

CONFIDENTIAL Page 95 of 139

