# **Secondary Endpoint: Status for exacerbation free over the 52-week treatment period**

```
PROC LOGISTIC DATA=<dataIn>;
  CLASS trtn(REF='3')
       region1(REF='North America')
        numpes (REF='>=3')
       psaecol(REF='Negative')
        agegr3(REF='Adult');
 MODEL statusn(EVENT='1') = trtp region1 numpes psaecol agegr3 /
    CLODDS=WALD ORPVALUE;
  ODDSRATIO "COMPARISON" trtp / DIFF=ALL CL=WALD ;
  ODS OUTPUT ODDSRATIOSWALD=<dataOut> MODELANOVA=<dataOut>;
RUN;
              participants treatment (brensocatib 25mg, brensocatib 10mg,
 trtp
               stratification factor: North America, Europe, Japan, and
region1
               the Rest of the World
               stratification factor: sputum sample being classified as
 psaecol
               positive or negative for Pseudomonas aeruginosa at
              screening visit
              stratification factor: number of prior PEs [<3 or ≥3] in
numpes
              the previous 12 months
statusn status variable with 1=responder and 2=non-responder agegr3 age group: adult, adolescent
```

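### The QoL-B meaningful-change responder analysis (SAP 8.3.5.4) is referred to a logistic model without the baseline QoL-B score; adding that score would gain some power and needs no new data

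*SAP*

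**What the plan says.** **The responder analysis.** SAP 8.3.5.4 takes its threshold from the trial: "The meaningful change threshold (MCT) will be estimated from the ASPEN data by applying an anchor-based approach", with PGI-S and PGI-C as anchors and all treatment groups pooled. Adults without a baseline score are left out. Adults with a baseline score but no Week 52 score count as non-responders. For the model, the SAP says only that the analysis of "responder status will be similar to the main analysis approach for the secondary endpoint of Responder Status for exacerbation-free over the 52-week treatment period".

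**The model referred to.** SAP 8.3.2.1 states: "Responder status at Week 52 will be compared between treatment groups brensocatib vs. placebo using a logistic regression model including treatment group". It goes on to *Pseudomonas aeruginosa* status, prior exacerbations, region and age group. The code in Appendix I agrees: "MODEL statusn(EVENT='1') = trtp region1 numpes psaecol agegr3". Neither contains a baseline score, and 8.3.5.4 does not add one.

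**The continuous analysis of the same score.** SAP 8.3.5.1 fits a repeated measures model with treatment, visit, their interaction and the stratification factors "as fixed effects, and baseline value as covariate". It has no age-group term.

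**The score.** It is listed among the baseline characteristics in SAP 7.3 ("Baseline QoL-B Respiratory Symptoms Domain Score (adults"). Appendix A gives its range: "Each of the 8 domain scores is standardized on a 0 to 100-point scale".

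**The concern.** The model in 8.3.2.1 was written for an exacerbation endpoint, which has no baseline score to adjust for. Here the outcome is a dichotomised change from baseline. Change usually correlates negatively with the starting value, both through regression to the mean and because the scale has a ceiling: a participant who starts above 100 minus the threshold cannot respond on either arm. The baseline score is therefore likely to predict response, and it is available for everyone in the analysis.

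This analysis will be read as showing whether the QoL-B effect matters to patients. Without the covariate it has less power than the same data allow, and any chance difference in baseline scores between arms stays in the odds ratio. The continuous QoL-B, FEV1 and BEST change analyses (SAP 8.3.5.1, 8.3.3.1 and 8.5.1) all adjust for their own baseline.

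**Working it through.** **1. The plan's own figure.** None is given for this analysis. The only power figure is for the primary endpoint (Protocol 10.1): 90% with 540 per arm, rates 1.2 and 0.84, dispersion 1 and two-sided alpha 0.005. It reproduces:
- Var(log RR) = (1/1.2 + 1/0.84 + 2)/540 = 0.00745, so SE = 0.0863.
- Power = Φ(0.3567/0.0863 − 2.807) = 90.7%.

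It says nothing about QoL-B.

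**2. Inputs.** From the documents: 540 adults per arm (SAP 3.1). Assumed, because the documents give no values: baseline mean 60 and SD 18, change SD 16, mean placebo change 0, treatment shift 3.3, threshold 8, normal scores, two-sided 0.05. The correlation r is between **baseline and change**, in absolute value.

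**3. Without baseline.**
- Placebo responder rate: 1 − Φ(8/16) = 0.3085.
- Active responder rate: 1 − Φ((8 − 3.3)/16) = 0.3845.
- Log OR = ln(0.3845/0.6155) − ln(0.3085/0.6915) = 0.336.
- SE = √[1/(540 × 0.3085 × 0.6915) + 1/(540 × 0.3845 × 0.6155)] = 0.1285.
- z = 2.618, and power = Φ(2.618 − 1.96) = 74.5%.

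This does not depend on r.

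**4. With baseline, r = 0.5.** Logistic fits to a very large simulated data set, with responder rates of 0.2 to 0.5, give a relative efficiency of 1.18 to 1.20.
- Lower: Φ(2.618 × √1.18 − 1.96) = 81.2%.
- Upper: Φ(2.618 × √1.20 − 1.96) = 81.8%.

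The gain is 6.7 to 7.3 points. The log OR moves from 0.34 to about 0.40, while its SE **rises** from 0.129 to about 0.140. The ratio goes from 2.62 to 0.40/0.140 = 2.86. The power therefore comes from a conditional odds ratio further from 1, and not from a smaller standard error.

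**5. Over a range of correlations.** Power gain in points, from runs of 2,000 to 4,000 simulated trials without stratification factors (simulation error of about a point remains):

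| r | Complete data | 15% missing as non-response |
|---|---|---|
| 0.3 | 1.9 to 2.6 | 1.6 to about 2 |
| 0.4 | 3.2 to 5.5 | about 4 |
| 0.5 | 6.3 to 7.1 | 5.3 to 5.5 |
| 0.6 | 9.4 to 11.2 | 7.4 to about 8 |

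The 15% is also assumed. As a check on that column at r = 0.5:
- The responder rates become 0.85 × 0.3085 = 0.262 and 0.85 × 0.3845 = 0.327, so z = 0.312/0.134 = 2.323 and power is 64.2%.
- With relative efficiency 1.15, power is Φ(2.323 × √1.15 − 1.96) = 70.2%, a gain of 6.0 points and close to the simulated 5.3 to 5.5.

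**6. Which correlation.** With equal SDs, the baseline-to-change correlation is −√[(1 − ρ)/2], where ρ is the baseline-to-Week 52 correlation. So ρ = 0.3, 0.5 and 0.7 give −0.592, −0.5 and −0.387. The gain rises with r but falls with ρ. Varying the unadjusted power from 50% to 90%, the responder rate from 0.2 to 0.5 and missingness between 0% and 15%, the gain is 4.2 to 11.7 points at ρ = 0.3, 3.0 to 7.8 at ρ = 0.5 and 1.8 to 4.4 at ρ = 0.7.

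**7. Ceiling.** With a threshold of 8, nobody starting above 92 can respond. Under the assumed distribution that is 1 − Φ((92 − 60)/18) = 3.8% of participants.

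**The case against.** **The wording does not settle the covariates.** The SAP writes *same* when it means an identical model (8.3.3.3, 8.3.4.3, 8.3.5.3), and 8.3.5.4 says *similar*. The approach cannot be copied exactly anyway, because 8.3.2.1 multiply imputes missing status and 8.3.5.4 counts it as non-response. A reader might infer that the sponsor decided to exclude baseline; the text does not show that. What stands is that the only model referred to lacks the term and nothing supplies it, so it is either omitted or left to the programmer.

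**Age group is not a real defect.** A reader might infer that the plan would fit a constant term in an adults-only analysis. SAP 8.3.2.1 allows age group to be removed if it causes estimability problems, and the main QoL-B model omits it. It should be dropped explicitly for clarity only.

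**The adjusted odds ratio is a different quantity.** This is correct. It is conditional on baseline and larger in size than the unadjusted one, and the report should say so.

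**Little depends on it.** This is also correct. The analysis is outside the 12 hypotheses of SAP 6.3 and has no power target, and the tested QoL-B comparison already adjusts for baseline. The cumulative responder curves in 8.3.5.3 show every threshold, although for the On-IP estimand and without covariates.

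**540 per arm is an upper figure.** The questionnaire is given only where validated translations exist (Protocol 7.5.2), and adults without a baseline score are excluded.

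**Conclusion.** The point holds as a minor, free improvement. The model referred to in SAP 8.3.5.4 omits a baseline score that is collected, is required for inclusion and is used in the continuous analysis of the same endpoint. Adding it gains about 5 to 7 points of power at a baseline-to-change correlation of 0.5 in absolute value, and about 2 to 11 points over 0.3 to 0.6. The lower part of each range is more likely once missing Week 52 scores count as non-response. Every input except 540 per arm is assumed, so no single figure should be quoted as a property of the plan.

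Two stronger readings are not supported. A reader might infer that the QoL-B secondary endpoint itself is weakened; it is not, because its tested model includes baseline. A reader might also infer that the odds ratio is biased or that its standard error would shrink. Randomisation means that only chance imbalance is at issue, and the standard error rises with adjustment.

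**What to change.** In SAP 8.3.5.4, replace the cross-reference with the model itself: logistic regression with treatment, the three stratification factors and the continuous baseline QoL-B Respiratory Symptoms Domain Score, without age group because the analysis is in adults only, as in 8.3.5.1. Keep the existing missing-data rules, and add that the reported odds ratio is conditional on baseline.

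The cost is a sentence or two of SAP text and one covariate in the code, settled before unblinding. It needs no new data and loses no participants, since those without a baseline score are already excluded.
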